### 9.4 Inclusion criteria

To be included in the study, subjects must fulfil the following criteria:

1. Willing and able to give written informed consent for participation in the study.
2. Subjects who have used tobacco-based snus for  $\geq 1$  year, with a minimum weekly consumption of 3 or more cans, and  $\geq 90\%$  of the total nicotine consumption should have been tobacco-based snus.
3. Non-smoker (have smoked maximum 5 packages in total ever and have not smoked at all during the last year).
4. Healthy male or female subject aged  $\geq 21$  to  $\leq 55$  years.

5. Normal stimulated salivary secretion rate (>0.7 mL/min).
6. At least 24 own teeth remaining and overall good oral health, as judged by the Investigator.
7. Female subjects of child-bearing potential must be willing to use a sufficient contraceptive method for the duration of the study, this includes mechanical barrier (*e.g.*, a male condom or a female diaphragm), combined [estrogen and progestogen containing] hormonal contraception associated with inhibition of ovulation [oral, intravaginal, transdermal], progestogen-only hormonal contraception associated with inhibition of ovulation [oral, injectable, implantable], intra uterine device (IUD) or intra uterine system (IUS). Sexual abstinence is allowed when this is the preferred and usual lifestyle of the subject.

## 9.5 Exclusion criteria

Subjects must be excluded from the study if any of the following exclusion criteria are fulfilled:

1. A history of diagnosed hypertension or any cardiovascular disease, or ongoing manifestations of hypertension or any cardiovascular disease as judged by the Investigator.
2. Any surgical or medical condition, including abnormal salivation (also pharmaceutically induced), or history thereof, which, in the judgment of the Investigator, might interfere with the absorption, distribution, metabolism or excretion of the IP or may either put the subject at risk because of participation in the study, influence the results, or the subject's ability to participate in the study.
3. Subjects who are pregnant, breastfeeding, or intend to become pregnant during the course of the study.
4. A history of diagnosed severe allergy/hypersensitivity or ongoing manifestations of severe allergy/hypersensitivity to aroma compounds (including fragrances and/or flavorings), as judged by the Investigator.
5. Subjects with severe oral conditions such as open caries lesions, severe periodontal health, lesions in the soft tissues (apart from gingival hyperplasia related to the use of snus), or extensive prosthetic work (*e.g.*, several implants, partial denture, dental veneers).
6. Current or history of alcohol abuse and/or use of anabolic steroids or drugs of abuse, as judged by the Investigator.
7. Antibiotic use  $\leq 4$  weeks prior to the screening period.
8. Subjects who intend to change their nicotine consumption habit, including the intention to stop using nicotine products, within the next 4 months of the screening visit, as judged by the Investigator.
9. Subjects undergoing other dental treatment during the study period.
10. The Investigator considers the subject unlikely to comply with study procedures, restrictions, and requirements.

## 9.6 Restrictions during the study

The subjects must be willing to comply with the following restrictions during the entire study duration, *i.e.*, from screening (Visit 1) to the last treatment visit (Visit 5).

### 9.6.1 General restrictions

1. Subjects shall refrain from approximal tooth cleaning for 48 h and toothbrushing for 24 h prior to the treatment visits (Visit 2-Visit 5).
2. Subjects shall abstain from eating, drinking, chew gum, or any other mouth related procedures for 1 h prior to the treatment visits (Visit 2-5).
3. Subjects shall completely substitute their tobacco-based snus product for ZYN from the second treatment visit (Visit 3) and abstain from all other nicotine products until the end of the study (Visit 5).
4. Subjects shall abstain from any drugs of abuse during the study, *i.e.*, from screening (Visit 1) to the last treatment visit (Visit 5).
5. Subjects shall abstain from alcohol for at least 12 h prior to each treatment visit (Visit 2-5).
6. Subjects shall use their regular toothbrush (electrical or manual) and the standard toothpaste containing fluoride (sodium fluoride-containing toothpaste; 1450 ppm F) from Visit 2 to Visit 5.
7. Subjects are not allowed to participate in any other clinical studies or use antibiotics during the study period, *i.e.*, from screening (Visit 1) to the last treatment visit (Visit 5).

### 9.6.2 Prior and concomitant therapy

Subjects undergoing other dental treatment during the study period will be excluded from the study. There will be no other restrictions concerning concomitant medications or therapies, as long as the subject is on a stable course of medication for the duration of the study. Prescribed medications taken *pro re nata* may be a reason for exclusion as judged by the Investigator if they affect the subject's general condition or salivation.

## 9.7 Screen failures

Screen failures are defined as subjects who consent to participate in the clinical study but are not subsequently visiting the clinic on the first treatment visit. A minimal set of screen failure information is required to ensure transparent reporting of screen failure subjects. Minimal information includes documentation of signed and dated informed consent form (ICF) and reason(s) for screening failure.

Rescreening can be performed if any of the following were reasons for screening failure or non-randomization (as judged by the Investigator):

- Practical reasons.
- Non-significant medical conditions (*e.g.*, influenza, nasopharyngitis).

For subjects who are rescreened, a new screening number will be assigned and a new, signed ICF will be collected.

## 9.8 Subject withdrawal

### 9.8.1 *General withdrawal criteria*

Subjects are free to discontinue their participation in the study at any time and for whatever reason without affecting their right to an appropriate follow-up investigation or their future care. If possible, the reason for withdrawal of consent should be documented.

Subjects may be discontinued from the study at any time at the discretion of the Investigator.

Reasons for discontinuation include:

1. Severe non-compliance with CSP procedures, as judged by the Investigator and/or Sponsor.
2. Subject is lost to follow-up. A subject will be considered lost to follow-up if he/she fails to come for consecutive scheduled visits and if he/she is not possible to be contacted by site staff despite several attempts.
3. Significant AE posing a risk for the subject, as judged by the Investigator and/or Sponsor.
4. Pregnancy.

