### 9.8.3 *Subject replacement*

Subjects who are prematurely withdrawn from the study may be replaced at the Sponsor's discretion after consultation with the PI. Subjects prematurely withdrawn due to AE(s) assessed as at least possibly related to the IP will not be replaced.

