## 9.9 Randomization

On Visit 3, the subjects will be randomized into two treatment arms (ZYN Dry or ZYN Moist). Within each treatment arm, the subjects can choose flavor and also change the selected flavor during the study. As this is an open-label study, the treatment arm to which each subject is allocated will be recorded in the eCRF. A computer-generated randomization list will be created using SAS Proc Plan, SAS Version 9.4 or later (SAS Institute, Inc., Cary, NC). The randomization list will contain subject number and treatment arm.

The randomization list will be generated by CTC and a copy of the randomization list will be provided to the packing company and to the clinic. The original randomization list will be kept by the randomizer.

Because this is an open-label study, no blinding procedures will be followed.

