### 17.1 General

Continuous data will be presented in terms of evaluable and missing observations, arithmetic mean, standard deviation (SD), median, minimum and maximum value, Q1-Q3 (interquartile range [IQR]).

Categorical data will be presented as counts and percentages. When applicable, summary data will be presented by each group (ZYN Dry or ZYN Moist), and by assessment time. Individual subject data will be listed by subject number, treatment arm (ZYN Dry or ZYN Moist), and, where applicable, by assessment time.

All descriptive summaries and statistical analyses will be performed using SAS Version 9.4 or later (SAS Institute, Inc., Cary, NC).

Baseline will be defined as the last data collected before subjects are randomized into substitution of tobacco-based snus with either ZYN Dry or ZYN Moist.

No adjustment for multiple comparisons will be made.

No imputation of missing data will be performed.

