### 17.3 Analysis data sets

#### 17.3.1 *Full analysis set*

The Full Analysis Set (FAS) will consist of all subjects who have been randomized. This population will be used as the safety analysis set.

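### Arm-aware removal for undefined severe non-compliance ends outcome measurement and allows discretionary replacement, so the plan permits selective loss from the Day 28 primary summary

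*Protocol*

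**What the plan says.** **Removal.** Section 9.8.1 states: "Subjects may be discontinued from the study at any time at the discretion of the Investigator". Its first listed reason is "Severe non-compliance with CSP procedures, as judged by the Investigator and/or Sponsor". The discontinuation is from the study, and Section 9.8 describes no route by which a subject breaches or stops product use and stays in follow-up. Section 9.6.1 makes complete substitution of snus from Visit 3, with no other nicotine products, a study restriction.

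**Who knows the arm.** Section 9.9: "Because this is an open-label study, no blinding procedures will be followed". The arm is recorded in the eCRF and the clinic holds a copy of the randomization list.

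**Data after withdrawal.** Section 9.8.2 asks for the reason and for any adverse events. It specifies no pH measurement.

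**Replacement.** Section 9.8.3: "Subjects who are prematurely withdrawn from the study may be replaced", at the sponsor's discretion after consulting the principal investigator. The one exception is withdrawal for an adverse event at least possibly related to the product. The arm that a replacement receives is not stated.

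**Analysis.** Section 17.3.1: "The Full Analysis Set (FAS) will consist of all subjects who have been randomized". Section 17.1: "No imputation of missing data will be performed". Under Sections 7.1.1 and 17.5.1 the primary endpoint is the difference between arms in the 4-week change in plaque acidogenicity, shown as summary statistics of AUC6.2. Section 17.6.1 takes the change from Visit 3 to Visit 5.

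**The concern.** Section 8.2 relies on randomization to limit bias and balance the arms. A decision taken after randomization, by people who know the arm and without a fixed criterion, can undo that balance if it determines who has a Day 28 value. A subject who dislikes the allocated product may be more likely to go back to snus, and going back breaches Section 9.6.1. If that happens more often with one product, and such subjects are removed, the Day 28 summaries compare differently selected groups.

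Even a balanced loss matters for the within-arm change in Section 17.6.1, because dropping relapsers moves each arm's mean towards the change in those who stayed on product. A later SAP can choose a model or an analysis set, but it cannot recover Day 28 measurements that were never taken.

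**Working it through.** **1. The plan's own loss figure.** Section 17.2 goes from 40 evaluable to 46 randomized at 15% dropout. 40 × 1.15 = 46 reproduces this. The loss implied is 46 − 40 = 6 subjects, or 6/46 = 13%. (Dividing instead, 40/0.85 = 47.1, and 46 × 0.85 = 39.1; the difference is immaterial here.) Section 9.3 gives 23 per arm. Six losses are used below.

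**2. What a removed subject contributes.**

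| Step | Section | Consequence for a subject removed before Visit 5 |
|---|---|---|
| Leaves the study | 9.8.1 | No Visit 5 |
| Reason and adverse events asked | 9.8.2 | No Day 28 pH |
| All randomized in the FAS | 17.3.1 | Counted by name |
| No imputation | 17.1 | No value for the 4-week change |
| Replacement allowed | 9.8.3 | Restores the number, not the lost outcome |

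A subject removed after Visit 4 still has Day 14 data, which Section 17.1 presents by assessment time.

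**3. Bias formula.** In one arm, mean of kept − mean of all randomized = (lost/23) × gap, where gap is the mean change in kept minus lost subjects. The bias in the difference between arms is (lost in A − lost in B)/23 × gap, with the same gap in both arms.

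**4. Assumptions not in the protocol.** All six losses fall under the non-compliance rule, and the gap is 1 SD of the AUC6.2 change. No SD, effect size or split is given in the protocol.

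**5. Standard error of the difference at 20 per arm.** √(2/20) = 0.32 SD.

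| Split of 6 losses | Bias, gap 1 SD | Share of SE | Bias, gap 0.5 SD |
|---|---|---|---|
| 3 vs 3 | 0 | 0 | 0 |
| 4 vs 2 | 2/23 = 0.09 SD | about 27% | 0.04 SD |
| 5 vs 1 | 4/23 = 0.17 SD | about 55% | 0.09 SD |

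**6. Fewer losses under this rule.** Suppose that 3 of the 6 fall under it and the other losses resemble the kept subjects. A 2 vs 1 split with a 1 SD gap then gives 1/23 = 0.04 SD.

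**7. Within-arm change.** At 3 vs 3 with a 1 SD gap, each arm's mean change is shifted by 3/23 = 0.13 SD although the difference between arms is unbiased. On a scale where compliers change by 1 unit and removed subjects would have changed by 0 to 0.5, the all-randomized mean would be 0.87 to 0.94, while the observed mean is 1.

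**The case against.** A reader might infer that the all-randomized analysis becomes an on-product completer analysis. The documents do not support that. Removal is permitted, not required, and is limited to severe cases. Nothing says that a return to snus must lead to removal. The FAS has no compliance filter, and fully evaluable in Section 9.3 is a recruitment target, not an analysis set. Compliance rests on asking subjects and on self-registered use (Section 10.5), so relapsers who are undetected or not removed, and who attend Visit 5, contribute a value.

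A reader might also infer that the sponsor can remove subjects alone. Section 9.8.1 places discontinuation at the investigator's discretion and names the sponsor in judging non-compliance; the and/or leaves the sponsor's part open without going that far.

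Four further objections carry weight:

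- The stated aim (Sections 6.2 and 8.1) concerns users who completely substitute, so interest in the on-product effect is legitimate.
- The planned dropout also covers withdrawn consent, loss to follow-up, adverse events and pregnancy, so charging all of it to this clause gives an upper illustration.
- The protocol's primary analysis is descriptive and states no test, so the harm is a biased estimate, not an inflated type I error. The standard error serves only as a scale.
- The choice of model belongs to the SAP. Replacement keeps the withdrawn subject in the FAS and adds nothing to the bias computed here.

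These points limit the size and the wording. They leave the main one standing: the protocol provides for removal with the arm known and for no outcome measurement afterwards. An interest in complete substitution does not remove the need to know what happened to randomized subjects who did not manage it.

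**Conclusion.** The concern holds as a statement about what the plan allows. Sections 9.8.1 to 9.8.3, with Sections 17.1 and 17.3.1, permit arm-aware selective loss from the Day 28 primary summary through an undefined criterion. Both the Dry versus Moist comparison and the within-arm change can be biased. On the labelled assumptions the bias in the comparison runs from nothing to roughly half a standard error across the splits shown. It shrinks with a smaller gap or with fewer losses under this rule. The protocol gives no data from which to choose among these values. The issue should be corrected because the loss cannot be repaired at the analysis stage.

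**What to change.** - **Sections 9.8.1 and 9.8.2:** state that non-compliance with snus substitution does not by itself end follow-up. Willing subjects attend Visits 4 and 5 for pH and the other scheduled assessments, and their consumption continues to be recorded. The other grounds for withdrawal are untouched.
- **Section 9.8.1:** take the sponsor out of the non-compliance judgement, and define severe for whatever non-compliance can still lead to removal.
- **Section 9.8.3:** drop discretionary replacement, since 46 already carries a dropout allowance. Otherwise give any replacement the next number on the randomization list and keep the replaced subject in the FAS.
- **Reporting:** present all randomized subjects with data, and beside them an on-product summary, because the stated aim concerns complete substitution. Leave the choice of model to the SAP.

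The cost is protocol wording, since the visits and consumption recording are already planned. The downside is that relapsers may dilute the estimate, which the on-product summary would show. The change does not retain subjects who withdraw consent or cannot be reached, and the investigator still knows the arm.

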### 9.8.2 *Procedures for discontinuation of a subject from the study*

If a subject withdraws consent or prematurely discontinues participation in the study, they will always be asked about the reason(s) for discontinuation/early withdrawal and the presence of any AEs. Any ongoing AEs will be followed as described in Section [11.6.10](#).

The primary reason for discontinuation/early withdrawal must be specified in the eCRF. If the primary reason in an AE, the AE must be specified.

### 9.8.3 *Subject replacement*

Subjects who are prematurely withdrawn from the study may be replaced at the Sponsor's discretion after consultation with the PI. Subjects prematurely withdrawn due to AE(s) assessed as at least possibly related to the IP will not be replaced.

## 9.9 Randomization

On Visit 3, the subjects will be randomized into two treatment arms (ZYN Dry or ZYN Moist). Within each treatment arm, the subjects can choose flavor and also change the selected flavor during the study. As this is an open-label study, the treatment arm to which each subject is allocated will be recorded in the eCRF. A computer-generated randomization list will be created using SAS Proc Plan, SAS Version 9.4 or later (SAS Institute, Inc., Cary, NC). The randomization list will contain subject number and treatment arm.

The randomization list will be generated by CTC and a copy of the randomization list will be provided to the packing company and to the clinic. The original randomization list will be kept by the randomizer.

Because this is an open-label study, no blinding procedures will be followed.

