## 8.2 Rationale for study design

This is an open-label, two-armed, randomized, longitudinal study, designed to assess the effects on dental plaque acidogenicity and other oral variables in current, daily tobacco-based snus users who completely substitute their snus with either ZYN Dry or ZYN Moist NPs.

A parallel study design was chosen for comparison of two types of ZYN product categories, ZYN Dry and ZYN Moist.

Randomization will be used to minimize bias in the assignment of subjects to one of the two treatment arms and to increase the likelihood that known and unknown subject attributes (*e.g.*, demographic and baseline characteristics) will be evenly balanced.

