### 9.2 Screening and enrolment log

The PI must keep a record of all screened subjects even if they were not subsequently included in the study. This information is necessary to verify that subjects were selected without bias. The reason for screening failure should be stated for all subjects that were screened but not included. The reason for withdrawal should be stated for all subjects that were included but did not complete the study.

A screening number will be allocated to each subject in connection to the informed consent process at the screening visit (Visit 1). The screening number is generated automatically in the electronic case report form (eCRF). The screening number will allow identification of subjects irrespective of their eligibility for the study.

Subjects included and randomized will be assigned a randomization number (101, 102 *etc.*).

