### 10.4 Preparation and accountability

The IPs will be distributed according to the randomization list by the site personnel. The Investigator will maintain a storage and accountability log as well as a distributing log detailing the dates and quantities of study IPs provided to each subject, as well as any IPs returned to the Sponsor at the end of the study. Products deliberately and/or accidentally destroyed by the site or the subject must be accounted for.

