#### 11.2.5 *Eligibility criteria*

Eligibility criteria should be checked during screening and verified before randomization on Visit 3. The criteria are specified in Sections [9.4](#) and [9.5](#).

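### The clinic receives a copy of the full randomization list, so the next allocation is knowable on site before the decision to randomize and before baseline is recorded

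*Protocol*

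**What the plan says.** Section 9.9 has the contract research organisation (CTC) generate the list. It states: "The randomization list will contain subject number and treatment arm". It then states that "a copy of the randomization list will be provided to the packing company and to the clinic", while the original stays with the randomizer. On masking it says: "Because this is an open-label study, no blinding procedures will be followed".

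Section 10.4 shows how the clinic uses its copy: "The IPs will be distributed according to the randomization list by the site personnel".

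Section 9.2 describes the numbering: "Subjects included and randomized will be assigned a randomization number (101, 102" (the series continues).

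Section 11.2.5 sets the last eligibility check: "Eligibility criteria should be checked during screening and verified before randomization on Visit 3". Several criteria in Section 9.5 rest on judgment, for example: "The Investigator considers the subject unlikely to comply with study procedures, restrictions, and requirements".

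Section 8.2 gives the reason for randomizing: "Randomization will be used to minimize bias in the assignment of subjects to one of the two treatment arms".

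**The concern.** Blinding and allocation concealment are separate safeguards. Blinding concerns what is known after a subject has been assigned. Concealment concerns what is known before. An open-label trial gives up the first but can keep the second in full. Section 9.9 waives blinding, and its custody rule for the list also leaves concealment unprotected.

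Two things are at stake.

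- **Who enters which arm.** If the next arm can be seen, a borderline eligibility judgment, the order of Visit 3 appointments, or a decision to postpone and rescreen can follow it, consciously or not. The protocol supplies an innocent motive: Section 9.3 aims for at least 5 women per arm, and Section 9.9 mentions no stratification by sex.
- **The baseline itself.** Section 8.1 places the Visit 3 assessments before randomization on the same day. Section 17.1 makes the last pre-randomization data the baseline, and the primary endpoint is a change from it. Some readings involve judgment: plaque scored 0-3, lesions graded 1-4, visual tooth shade, and the fallback pH strip read against a colour scale. In an open-label trial, concealment is what keeps these readings independent of arm.

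Analysis cannot fully repair selection on unmeasured factors.

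**Working it through.** The protocol states no figure on this point, so there is none to reproduce. The check is a reading of the sections together, followed by two illustrations.

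**1. The sections side by side**

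- The list shows arm in clear against subject number (9.9).
- The clinic has a copy (9.9), and site personnel dispense from it (10.4). No delivery date is given, but the copy must be on site by the first Visit 3 handout.
- Numbers run 101, 102 and so on (9.2). Assignment in running order is the natural reading, though it is not stated. On that reading the next unused line is the next arm.
- Eligibility is verified at Visit 3 before randomization (11.2.5), and baseline readings are taken earlier in the same visit (8.1).
- The protocol mentions no sealed envelopes, no release of the arm through the eCRF, and no restriction of the list to staff outside enrolment.

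It follows that the next arm is knowable on site before the decision to randomize and before baseline is complete.

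**2. How predictable is the next arm?**

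Input from the protocol: 46 randomized, 23 per arm. Assumption: a simple 23:23 random list, because block structure is not stated.

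- List on site: up to 46 of 46 (100%).
- List withheld, staff see past open-label allocations and guess the arm that is behind. With n per arm, expected correct guesses = n + (2^(2n)/C(2n,n) − 1)/2. For n = 23 this is 23 + (8.547 − 1)/2 = 26.77, and 26.77/46 = 58%.
- List withheld, permuted blocks of four (assumed, block size known to the guesser): n = 2 gives 2 + (16/6 − 1)/2 = 2.83 of 4, or 71%.

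**3. What could that do to the comparison? (hypothetical)**

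The protocol gives no SD, effect size or alpha, so these figures rest on assumed inputs.

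*Steering model.* Suppose a subject's expected outcome is shifted by +η or −η SD according to the guessed arm, and the guess is right with probability p. The spurious arm difference is 2η(2p − 1).

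| η (assumed) | List on site, p = 1 | Withheld, 23:23, p = 0.582 | Withheld, blocks of four, p = 0.708 |
|---|---|---|---|
| 0.1 SD | 0.20 | 0.03 | 0.08 |
| 0.3 SD | 0.60 | 0.10 | 0.25 |

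*Rejection model.* Suppose that when one arm is next, a fraction q of all candidates is turned away, all from the worst 30% of a normal prognostic variable. That group's mean is 0.348/0.3 = 1.159 SD, so those kept shift by q × 1.159/(1 − q): 0.061, 0.129 and 0.290 SD for q = 5%, 10% and 20%. For scale, the 95% confidence half-width with 20 against 20 is 2.024 × √(2/20) = 0.64 SD. The two are directly comparable only if prognosis and outcome are perfectly correlated. The model also rejects candidates outright and does not move them to the other arm.

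**The case against.** The strongest objection is that the text does not show anyone with enrolment authority looking at the list. Section 9.9 says only that the clinic gets a copy. Section 10.4 speaks of site personnel, and Section 11.2.5 does not say who verifies eligibility. A reader might infer that the list goes to the very staff who confirm eligibility, so that the next arm is known to them and concealment is lost. The documents do not support that: they name no holder of the copy and no use of it beyond dispensing. What they support is that the arm is knowable and that nothing described prevents access.

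The protocol also limits the room for steering. Before Visit 3 a subject has passed screening, had eligibility confirmed at Visit 2 (Table 8.1-1) and completed a 28-day run-in. Visit windows are ±2 days (11.1), eligibility waivers are barred (Section 9), and reasons for screening failure and withdrawal must be logged (9.2). These controls stand and reduce the risk. They do not remove it, because Section 9.7 allows rescreening after non-randomization for practical reasons as judged by the Investigator, and a log of reasons cannot show whether order or postponement followed the list.

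Two further points stand. Both arms are the sponsor's own products and the primary analysis is descriptive (17.5.1), so the motive to steer is weaker than in a confirmatory trial against a competitor. And withholding the list would not make the next arm unpredictable at a single open-label site, as the 58% and 71% figures show.

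Open-label status is not an answer, since concealment before assignment is achievable without blinding. Nor is this a matter usually left to a statistical analysis plan: custody of the list is trial conduct, and Section 9.9 fixes it.

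**Conclusion.** The point holds as a weakness in the stated custody rule and should be fixed. Sections 9.9 and 10.4 place an unmasked, running list at the site where eligibility is verified and baseline is measured, with no described safeguard. This works against the purpose stated in Section 8.2.

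In size, up to 46 of 46 allocations are knowable, against roughly 58% to 71% guessable with the list withheld, depending on the assumed list structure. The conclusion rests on numbers being used in running order and on there being no access restriction outside the protocol.

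A reader might go further and conclude that the arm comparison is biased, by a few tenths of an SD. The protocol does not support that. The steering and rejection rates behind the SD figures are assumptions, and a shift in prognosis may carry over only partly to a change from baseline.

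**What to change.** - **Section 9.9:** remove the clinic as a recipient of the list. Keep it with the randomizer at CTC. Release one allocation at a time, only after eligibility is confirmed and the Visit 3 baseline assessments are recorded. Release can go through the eCRF, which already records the arm, or by sequentially numbered opaque sealed envelopes, or by request to the randomizer. The site may receive the full list once the last subject is randomized.
- **Section 10.4:** have site personnel distribute product according to the released allocation. Without this change the two sections would conflict.
- If the list is blocked, do not disclose the block size to the site. Some predictability from past allocations will remain.

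The cost is an amendment to two sections, setting up the release procedure, and a short extra step per subject at Visit 3. Sample size, visits and analysis are unaffected.
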